## 11.2 Population to be analysed

The primary analysis of all outcome data will be an intention-to-treat (ITT) analysis including all randomised participants, regardless of whether they received trial drug.

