## Оитсомея Primary outcomes: 1. Symptomatic COVID-19 defined as: AND OUTCOME **MEASURES** a positive SARS-CoV-2 test (PCR, RAT or serology) over the 6 months following randomisation PLUS • fever (using self-reported questionnaire)OR • at least one sign or symptom of respiratory disease, including cough, sore throat, shortness of breath, respiratory distress/failure (using self-reported questionnaire) 2. Severe COVID-19 defined as: a positive SARS-CoV-2 test (PCR, RAT or serology) over the 6 months following randomisation PLUS • Death (as a consequence of COVID-19) • Hospitalised (including mechanical ventilation and death), OR Non-hospitalised severe disease, defined as Non-ambulant for $\geq$ 3 consecutive days OR Unable to work for $\geq$ 3 consecutive  "pretty much confined to bed (meaning finding it very difficult to do any normal daily activities"  "I do not feel physically well enough to go to work" Secondary outcomes: All assessed at 6 and 12 months following randomisation unless otherwise indicated. The following outcomes are for both COVID-19 and fever or respiratory illness: presence of disease, days unable to work, days confined to bed, of days with symptoms, pneumonia, need for oxygen therapy, admission to critical care, need for mechanical ventilation Symptomatic or severe COVID-19, fever or respiratory illness Time to first symptom of COVID-19, fever or respiratory illness Deaths Number of days of unplanned absenteeism Type and severity of local and systemic adverse event over the 3 months following randomisation Planned exploratory analyses: episodes of and time to first recurrence of herpes simplex recurrence, immunological studies 7244 adult healthcare workers from Brazil, Europe and Australia TRIAL **POPULATION** (Victoria, Western Australia, South Australia and New South Wales) will be involved in the study, plus 2834 recruited in the earlier stage of this study. Key exclusion criteria are having BCG vaccine

contraindication, previously had a SARS-CoV-2 positive test result and prior involvement in this trial at an alternate study site. Participants will be randomised at 1:1 ratio giving approximately 5039 per group.

Multiple sites will enrol healthcare workers in Brazil, Europe and

Study Name: BCG vaccination to Reduce the impact of COVID-19 in healthcare workers (BRACE) trial RCH HREC number: 62586

Australia.

Version & date: version 12.0 dated 17May2022

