## 3.1.2 Secondary objectives

3. To determine if BCG vaccination (Intervention) compared with placebo (Comparator) reduces the incidence of symptomatic COVID-19 (Outcome) measured over the 12 months following randomisation (Time) in healthcare workers (Participants).

 $^{1}$  "pretty much confined to bed (meaning finding it very difficult to do any normal daily activities"

<sup>2"I do not feel physically well enough to go to work"

- 4. To determine if BCG vaccination (Intervention) compared with placebo (Comparator) reduces the incidence of severe COVID-19 (non-hospitalised severe disease, hospitalisation or death) (Outcome) measured over the 12 months following randomisation (Time) in healthcare workers (Participants).
- 5. To determine if BCG vaccination (Intervention) compared with placebo (Comparator) prolongs the time to first COVID-19 episode (Outcome) measured over 6 and 12 months following randomisation (Time) in healthcare (Participants).
- 6. To determine if BCG vaccination (Intervention) compared with placebo (Comparator) reduces the severity of COVID-19 (Outcome) measured over 6 and 12 months following randomisation (Time) in healthcare workers (Participants).
- 7. To determine if BCG vaccination (Intervention) compared with placebo (Comparator) reduces the rate and severity of illness (fever or at least one sign or symptom of respiratory disease) measured over 12 months following randomisation (Time) in healthcare workers (Participants).
- 8. To determine if BCG vaccination (Intervention) compared with placebo (Comparator) reduces absenteeism (days off work) over 6 and 12 months following randomisation (Time) in healthcare workers (Participants).
- 9. To evaluate the safety of BCG vaccination in healthcare workers.

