8. To determine if BCG vaccination (Intervention) compared with placebo (Comparator) reduces absenteeism (days off work) over 6 and 12 months in healthcare workers (Participants).	Number of days of unplanned absenteeism for an acute illness or hospitalisation (using self-reported questionnaire) within 6 and 12 months following randomisation
9. To evaluate the safety of BCG vaccination in healthcare workers.	Adverse events (AEs), over the 3 months following randomisation, by type, severity (graded using toxicity grading scale), relationship to intervention of adverse events (AEs) of interest.
	Serious Adverse Events, over the 3 months following randomisation
Exploratory analyses	
10. To determine in a subgroup of participants with recurrent cold sores whether BCG vaccination compared	Herpes simplex recurrences (self-reported) over the 12 months following randomisation
with placebo reduces herpes simplex recurrence (such as cold sores) .	Number of episodes of herpes simplex recurrence (self-reported) over the 12 months following randomisation
	Time: to first of herpes simplex recurrence (self-reported) over the 12 months following randomisation
To determine the BCG vaccination-induced changes in the immune system that are associated with protection against non-tuberculous infectious diseases including COVID-19.  12. To determine and compare changes in the immune system induced by vaccination.	The immune system will be assessed by several methods including:  - Cytokine levels in supernatants from whole blood stimulated with off-target pathogens (including BCG, Staphylococcus aureus, Escherichia coli) and Toll-like receptor (TLR) agonists, measured by multiplex  - Cytokine production, activation and differentiation of immune cells (measured by flow cytometry)  - Epigenetic modifications (e.g. histone methylation/acetylation and CpG methylation) measured by ChIP-Seq and/or microarray  - Anti-vaccine and anti-pathogen (including SARS-CoV2) antibody levels measured by ELISA, multiplex or VirScan  - RNA expression measured by qRT-PCR or RNA-Seq

Study Name: BCG vaccination to Reduce the impact of COVID-19 in healthcare workers (BRACE) trial

RCH HREC number: 62586

Version & date: version 12.0 dated 17May2022

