## 5.2.9 Discontinuation from trial intervention

The trial intervention is a once-off vaccination. Due to this there is no possibility to 'discontinue the trial intervention'. If a participant changes their mind between randomisation and vaccination, deciding that they do not want to have the vaccination (but are happy to continue in the study for the follow-up period) they will be included in the analysis as intention to treat.

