#### 8 SAFETY MONITORING AND REPORTING

#### 8.1 Definitions

## Adverse Event (AE):

An AE is any untoward medical occurrence in a participant administered an investigational product and does not necessarily have a causal relationship with the study treatment. For this study, only certain adverse events are recorded, specifically serious adverse events as defined below, and non-serious adverse events of interest specified in section 8.2

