## 11.3 Methods of analysis

Data analysis for the study will be performed by CEBU at MCRI. [name] has been appointed for the trial.

Statistical analysis will follow standard methods for randomised trials and the primary analysis will be by intention to treat (ITT), including all randomised participants.

Categorical variables will be presented as the number and proportion in each category. Continuous variables will be presented as means and standard deviations (SDs), or medians and interquartile ranges for skewed data, and the range.

PRIMARY ANALYSIS. Comparison between the BCG and placebo groups in the proportions of participants with symptomatic COVID-19 (primary outcome 1), as well as in the proportions of participants with severe COVID-19 (primary outcome 2), will be presented as the absolute risk difference (RD) as well as the risk ratio (RR) at 6 months and their 95% confidence interval (CI), obtained using a generalised linear model, with adjustment for the strata (defined by site, age and presence of comorbidity) used in the randomisation. The same analysis will be repeated on the same outcomes at 12 months. As secondary analyses the same models will be run to include also the following covariates: gender, number and type of comorbidities, whether already vaccinated for BCG in the past, and any other factor that may show imbalance between the groups at baseline.

A secondary analysis will be performed as above on the total 10078 participants, comparing all the participants who were randomised to BCG (irrespective of whether they received influenza vaccine at randomisation) and those randomised to control (irrespective of whether they received influenza vaccine or placebo at randomisation). Analysis will be as described above, but also adjusted for being in the initial stage of the study. As part of this analysis we will conduct an exploratory analysis of whether the treatment effect varies between the two stages of the study (prior to and post the introduction of the placebo) by including an

interaction between treatment and study stage. Results will be interpreted with caution given that the study is underpowered for this comparison.

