SECONDARY OUTOMES. According to the nature of the secondary outcomes to be analysed (binary, continuous or categorical) the appropriate generalised linear model (GLM) will be used to estimate the effect of the BCG vaccine on the outcome of interest compared to the control group. All analyses will be adjusted for the stratification factors used in the randomisation (site, age and presence of comorbidity). As secondary analyses the same models will be run to include the following covariates: sex, number and type of comorbidities, whether already vaccinated for BCG in the past, and any other factor that may show imbalance between the groups at baseline.

Survival analysis techniques will be adopted to analyse time to event data.

A secondary analysis will be conducted on the total 10078 participants using the same methodology but also adjusted for being in the initial stage of the study. We will conduct an exploratory analysis of whether the treatment effect varies between the two stages of the study by including an interaction between treatment and study stage.

Sub-group analyses will be undertaken on outcomes of those who:

- Had previous BCG vaccine before enrolling into the trial
- Had a positive serology to SARS-CoV-2 when enrolling into the trial

The full details for each variable will be included in the Statistical Analysis Plan (SAP).

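### Section 11.2 puts the primary safety analysis on an intention-to-treat basis, so adverse events are attributed to the product assigned and not the product received

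*Protocol*

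**What the plan says.** Protocol section 11.2 gives one rule: "The primary analysis of all outcome data will be an intention-to-treat (ITT) analysis including all randomised participants, regardless of whether they received trial drug". Section 11.3 repeats it for the methods: "the primary analysis will be by intention to treat (ITT), including all randomised participants".

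Safety is among the outcomes this covers. Objective 9 in section 3.1.2 reads "To evaluate the safety of BCG vaccination in healthcare workers". The outcome table in section 3.2 lists, for that objective, adverse events of interest and "Serious Adverse Events, over the 3 months following randomisation". The synopsis lists as a secondary outcome "Type and severity of local and systemic adverse event over the 3 months following randomisation".

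Section 5.2.9 deals with participants who change their mind after randomisation, decline the injection and stay in follow-up: "they will be included in the analysis as intention to treat". It makes no distinction between efficacy and safety.

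Section 8.1 ties the adverse event itself to receipt: "An AE is any untoward medical occurrence in a participant administered an investigational product".

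**The concern.** For a superiority question on efficacy, analysing everyone as randomised is standard, and the dilution it brings works against the intervention. For a harm question the same dilution works in the intervention's favour, because it makes the product look safer than it is in those who received it.

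Two groups matter. Someone assigned to BCG and never injected cannot have an injection-site abscess, a large ulcer, a keloid scar or disseminated BCG infection, yet is counted in the denominator for all of them. Someone given the wrong product has any reaction to it counted under the other product.

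The protocol also does not line up with itself. Most non-serious events of interest in section 8.2 presuppose an injection, as does the definition in section 8.1, while section 11.2 takes the denominator without regard to injection.

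Safety is a real aim of this trial. Section 2.3.1 names documenting the safety of vaccination and revaccination as an aim. Section 2.3.3 says BCG is used outside its recommended use and that reactogenicity and safety will be assessed for that reason. The rate a reader needs is the rate per person injected.

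**Working it through.** The protocol states no figure on this point, so there is none to reproduce. The check has a textual step and a size step.

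**Does the rule reach safety?** Section 11.2 refers to all outcome data. Section 3.2 and the synopsis both list adverse events as outcomes. Sections 5.2.9 and 11.3 repeat intention to treat without exception. No section defines a safety or as-received population. Read as written, the rule reaches safety.

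**Inputs for size**
- BCG group in Stage 2: 3622 (section 11.1).
- Illustrative reaction rates after BCG, p: up to 10% (swollen axillary nodes), up to 1 in 100 (uncommon effects) and up to 1 in 1000 (rare effects), all from section 2.3.1.
- Rate without BCG, c: taken as 0 for local reactions, since section 2.3.1 says saline causes none.
- Share of the BCG group not injected, q: not in the protocol. Assumed 1% to 3%, with 0.5% to 5% as a wider range.
- Share of the placebo group given BCG in error, x: not in the protocol. Assumed 0.1% to 1%.

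**Non-receipt.** Assume that uninjected participants have the control rate c, and that the placebo group also has rate c.

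ITT rate in the BCG arm = p(1 − q) + cq

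ITT risk difference = p(1 − q) + cq − c = (p − c)(1 − q)

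The risk difference therefore shrinks by exactly the fraction q, whatever p and c are.

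| p | q | ITT rate (c = 0) | Events in 3622, ITT | Events if all injected |
|---|---|---|---|---|
| 10% | 0.5% | 9.95% | 360.4 | 362.2 |
| 10% | 1% | 9.9% | 358.6 | 362.2 |
| 10% | 3% | 9.7% | 351.3 | 362.2 |
| 10% | 5% | 9.5% | 344.1 | 362.2 |
| 1% | 1% | 0.99% | 35.9 | 36.2 |
| 1% | 5% | 0.95% | 34.4 | 36.2 |

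**Wrong product.** Expected BCG reactions counted under placebo = 3622 × x × p, for x from 0.1% to 1%:
- p = 10%: 0.36 to 3.6 events
- p = 1%: 0.04 to 0.36 events
- p = 0.1%: 0.004 to 0.036 events

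Both mechanisms act towards no difference. An analysis of injected participants by product received removes both.

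**The case against.** The best reply is that the sentence fixes less than it seems to. It governs the primary analysis, so an added as-received safety table is not forbidden. Section 11.3 leaves the details for each variable to the statistical analysis plan, and safety populations are often defined there. This stands in part: a reader might infer that the protocol rules out any analysis by product received, and it does not. But the population is not left open. The protocol sets it, expressly for all outcomes, and an analysis plan that made as-received the primary safety analysis would depart from section 11.2.

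A second reply is that capture is already tied to receipt. Section 5.2.6 records the batch and time of each injection and requires variations in administration to be documented. Section 8.4 requires a causality grade for each event, and section 10.1.3 provides an independent safety monitor. A BCG complication in someone assigned to placebo could be traced. That stands for individual cases. It does not settle which denominator and which arm the reported rates use.

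A third reply is that the effect is small. There is a single injection, randomisation takes place on the day of enrolment, and trained clinicians give the dose. This stands.

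A reader might still infer a serious threat to rare events: at 1 in 1000, 3622 recipients give 3.6 expected events, and one misplaced event would be 1/3.6, or about 28%, of the signal. The documents do not support using that figure. It presumes that a wrong-product injection and a rare complication have already coincided in one person, the 1 in 1000 is an upper bound, and the expected number of such events under the assumed error rates is only 0.004 to 0.036.

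**Conclusion.** The point holds as a stated rule that does not suit safety outcomes. Section 11.2 counts uninjected BCG-assigned participants in the denominator of BCG reaction rates and counts wrong-product recipients in the arm assigned, in tension with the definition in section 8.1.

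The bias is towards no difference. Its size is probably small: a relative reduction of about 1% to 3% in the risk difference if 1% to 3% of the BCG arm is not injected, and 5% at the top of the wider range. These shares are assumptions, because the protocol reports neither non-receipt nor product errors. The calculation also assumes that uninjected participants have the control group's event rate.

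The primary outcomes, the alpha allocation and the sample size are not affected. The case for change rests on the direction of the error and the low cost of removing it, not on a large numerical effect.

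**What to change.** - In section 11.2, limit the intention-to-treat sentence to efficacy outcomes.
- Make the main analysis of objective 9 in Stage 2 an as-received analysis of injected participants, grouped by the product received.
- List participants not injected, or given the wrong product, separately with their events.
- Bring section 5.2.9 into line, so that keeping uninjected participants in the analysis refers to efficacy.
- In any safety analysis that pools the two stages, keep the Stage 1 controls as a no-BCG group. Section 11.1 shows that these 1417 participants had influenza vaccine and no placebo by design, so a rule restricted to recipients of a trial injection would drop all of them.
- An intention-to-treat safety table may be kept as supportive.

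The cost is a few sentences. No new data are needed, because the injection records in section 5.2.6 already exist. The downside is that the main safety comparison is no longer strictly by randomised group, which the supportive table would cover.

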## 11.2.1 Handling of missing data

For the primary analysis the imputation of missing data will only be considered if 10-20% of the primary outcome is missing and will be undertaken using multiple imputation (MI) models. Multiple imputation analysis will be performed on the ITT population. The frequency and patterns of missing data will be examined. Multiple imputation models will be conducted separately in the two treatment groups using chained equations applied to all outcomes, including baseline measures, as auxiliary variables. Fifty imputed datasets will be generated including all randomised subjects.

## 11.3 Methods of analysis

Data analysis for the study will be performed by CEBU at MCRI. [name] has been appointed for the trial.

Statistical analysis will follow standard methods for randomised trials and the primary analysis will be by intention to treat (ITT), including all randomised participants.

Categorical variables will be presented as the number and proportion in each category. Continuous variables will be presented as means and standard deviations (SDs), or medians and interquartile ranges for skewed data, and the range.

PRIMARY ANALYSIS. Comparison between the BCG and placebo groups in the proportions of participants with symptomatic COVID-19 (primary outcome 1), as well as in the proportions of participants with severe COVID-19 (primary outcome 2), will be presented as the absolute risk difference (RD) as well as the risk ratio (RR) at 6 months and their 95% confidence interval (CI), obtained using a generalised linear model, with adjustment for the strata (defined by site, age and presence of comorbidity) used in the randomisation. The same analysis will be repeated on the same outcomes at 12 months. As secondary analyses the same models will be run to include also the following covariates: gender, number and type of comorbidities, whether already vaccinated for BCG in the past, and any other factor that may show imbalance between the groups at baseline.

A secondary analysis will be performed as above on the total 10078 participants, comparing all the participants who were randomised to BCG (irrespective of whether they received influenza vaccine at randomisation) and those randomised to control (irrespective of whether they received influenza vaccine or placebo at randomisation). Analysis will be as described above, but also adjusted for being in the initial stage of the study. As part of this analysis we will conduct an exploratory analysis of whether the treatment effect varies between the two stages of the study (prior to and post the introduction of the placebo) by including an

interaction between treatment and study stage. Results will be interpreted with caution given that the study is underpowered for this comparison.

SECONDARY OUTOMES. According to the nature of the secondary outcomes to be analysed (binary, continuous or categorical) the appropriate generalised linear model (GLM) will be used to estimate the effect of the BCG vaccine on the outcome of interest compared to the control group. All analyses will be adjusted for the stratification factors used in the randomisation (site, age and presence of comorbidity). As secondary analyses the same models will be run to include the following covariates: sex, number and type of comorbidities, whether already vaccinated for BCG in the past, and any other factor that may show imbalance between the groups at baseline.

Survival analysis techniques will be adopted to analyse time to event data.

A secondary analysis will be conducted on the total 10078 participants using the same methodology but also adjusted for being in the initial stage of the study. We will conduct an exploratory analysis of whether the treatment effect varies between the two stages of the study by including an interaction between treatment and study stage.

Sub-group analyses will be undertaken on outcomes of those who:

- Had previous BCG vaccine before enrolling into the trial
- Had a positive serology to SARS-CoV-2 when enrolling into the trial

The full details for each variable will be included in the Statistical Analysis Plan (SAP).

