## 4 TRIAL DESIGN

## 4.1 Overall design

This is a phase III, two group, multicentre, randomised placebo-controlled trial in up to 7244 frontline healthcare workers to determine if BCG vaccine reduces prevalence and the severity of COVID-19 during the 2020, SARS-CoV-2 pandemic. As part of this study, we plan to combine the data from this study in a pre-planned meta-analysis with data from the 2834 participants recruited in the first stage of this study which followed the same protocol but where participants were randomised between BCG and no BCG at the time of receiving an influenza vaccination, for a total sample size of 10078. Although we recognise that the first stage of this study was addressing a slightly different research question, we feel that it is important to combine data from the first stage of study as they both provide estimates of the efficacy of the BCG vaccination, which is critical to provide adequate power to determine the efficacy of the BCG vaccination. In Europe, there will be participating sites in the Netherlands, Spain and UK. The sites participating in the Netherlands are Noordest Ziekenhuis Alkmaar, Rijnstate Hospital Arnhem, Amphia Hospital Breda, St Antonius Hospital Nieuwegein, Radboud UMC Nijmegen and Universitair Medisch Centrum Utrecht. In Spain, University Hospital German Trias I Pujol Barcelona, Mutua Terrassa Univeristy Hospital Barcelona, University Hospital Cruces Bizkaia, Marqués de Valdecilla University Hospital Santander and University Hospital Virgen Macarena Sevilla. In United Kingdom, Teign Estuary Medical Group Devon, Ide Lane Surgery Exeter, St Leonard's Practice Exeter, Travel Clinic Exeter and Royal Devon and Exeter NHS Foundation Trust Exeter.

In Australia, participating sites are hospitals within Victoria, Western Australia, South Australia and New South Wales. Australian sites involved in this study include the RCH VIC, Monash Health VIC, Epworth Healthcare VIC, Perth Children's Hospital WA, Fiona Stanley Hospital WA, Sir Charles Gairdner Hospital WA, Royal Adelaide Hospital SA, Women's and Children's Hospital Adelaide SA, The Children's Hospital at Westmead NSW, Westmead Hospital NSW, Prince of Wales Hospital NSW, St Vincent's Hospital Sydney NSW and Sydney Children's Hospital, Randwick NSW.

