For the primary outcome (2), severe COVID-19 at 6 months, we powered the study to identify a risk ratio of 0.67 in the BCG compared with the placebo group for severe COVID-19 at 6 months (which is much more realistic than a risk ratio of 0.5 as per the original sample size). Assuming that 4% of subjects will be infected by severe COVID-19 by 6 months in the control group, a total sample size of n= 6076 (3038 per group) will provide 80% power with 2-tailed 0.04 significance level (80% of the global significance level) for the Pearson chi-square test to detect a risk ratio of 0.667, equivalent to an absolute difference of 1.3%. Note this calculation was conducted using an alpha of 0.04 to allow the remaining 0.01 to be spent on primary outcome (1) (alpha=0.005) and the interim analysis as originally planned (alpha=0.005, see section 11.4 for details of the interim analysis, total alpha for this outcome=0.045). Allowing for a 16% loss to follow up, it is planned that the study will recruit 7244 healthcare workers.

In the pre-planned meta-analysis, we will have a sample size of 10,078 participants (7244+2834), or 8062 participants allowing for an overall 20% loss to follow up. For the combined analysis it is expected that the drop-out will be slightly higher (20% instead of 16%) because it also includes participants recruited prior to the introduction of the placebo, i.e. not placebo controlled. Again assuming that 4% of subjects will be infected by severe COVID-19 by 6 months in the control group, a total sample size of n=8062 (4031 per group) will provide 90% power with 2-tailed 0.04 significance level for the Pearson chi-square test to detect a risk ratio of 0.667, equivalent to an absolute difference of 1.3%. This will be a secondary analysis of the final study report.

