The original trial plan included a meta-analysis on all the outcomes (both COVID-19 and non-COVID-19 related outcomes) combining data from Stage 1 and Stage 2 participants. Stage 1 healthcare workers were recruited only in Victoria and Western Australia, both of which Australian states had almost negligible COVID-19 exposure risk during that trial period (30th Mar 2020 to 13th May 2020). In light of this, the overwhelming majority of Stage 1 blood samples are likely to be seronegative. Moreover, with a low prevalence of COVID-19, there is a high probability that positive SARS-CoV-2 serology results are false positive. For these reasons, in December 2021 the BRACE team has agreed that it is not justifiable to devote extra resources (time and costs) to the data cleaning of potential COVID-19 episodes and SARS-CoV-2 serology for all participants in Stage 1. As a consequence, the meta-analysis will

only be run on non-COVID-19 related outcomes and its main objective will be to determine if BCG vaccination compared with control reduces the rate and severity of febrile or respiratory illness over 12 months following randomisation in Stage 1 and Stage 2 healthcare workers.

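### Section 11.3 still orders pooled Stage 1 and 2 analyses of COVID-19 outcomes, and 11.1 still gives 90% power for one, after 11.1 itself limits pooling to non-COVID-19 outcomes

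*Protocol*

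**What the plan says.** **For pooling the COVID-19 outcomes**

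- Section 11.3, primary analysis, names two outcomes, symptomatic and severe COVID-19, and describes their models. It continues: "A secondary analysis will be performed as above on the total 10078 participants, comparing all the participants who were randomised to BCG" with those randomised to control, adjusted for stage and with an exploratory treatment-by-stage interaction.
- Section 11.3, secondary outcomes, repeats the order: "A secondary analysis will be conducted on the total 10078 participants using the same methodology". COVID-19 outcomes are not excepted, although many of the secondary outcomes in section 3.2 are COVID-19 outcomes.
- Section 11.1 sizes the pooled comparison of severe COVID-19 at 6 months. With 4% in controls and a risk ratio of 0.667, "a total sample size of n=8062 (4031 per group) will provide 90% power with 2-tailed 0.04 significance level". It adds: "This will be a secondary analysis of the final study report".
- Section 4.1 calls combining the stages "critical to provide adequate power to determine the efficacy of the BCG vaccination".

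**Against it**

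- The last paragraph of section 11.1 reports a decision of December 2021. Stage 1 recruited only in two Australian states with almost no COVID-19 exposure at the time, and "there is a high probability that positive SARS-CoV-2 serology results are false positive". The team judged it "not justifiable to devote extra resources (time and costs) to the data cleaning of potential COVID-19 episodes and SARS-CoV-2 serology" for all Stage 1 participants. The meta-analysis will therefore "only be run on non-COVID-19 related outcomes and its main objective will be to determine if" BCG reduces febrile or respiratory illness over 12 months.

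The synopsis announces the meta-analysis without saying which outcomes it covers.

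**The concern.** The same protocol version orders an analysis and withdraws it. An analyst who follows 11.3 would rerun both primary outcomes on all 10078 participants, using Stage 1 COVID-19 episodes and serology that 11.1 says will not be cleaned. An analyst who follows the end of 11.1 would omit a secondary analysis that 11.3 lists. Either course can be called a departure from the protocol.

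The pooled result would also mean little:

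- A stage with almost no true cases shrinks the crude risk difference, and 11.3 makes the risk difference a reported measure.
- False-positive cases, falling equally in both arms, would pull the risk ratio towards 1.
- A stage-adjusted risk ratio is little disturbed by a stage without events, but gains almost no power from it.
- The treatment-by-stage interaction could hardly be estimated for these outcomes.

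Meanwhile a reader of 11.1 may credit the trial with 90% power for severe COVID-19, through an analysis that has been dropped.

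**Working it through.** **Inputs from section 11.1.** Stage 2: 7244 randomised, 16% loss, 3038 per group needed for 80% power. Pooled: 7244 + 2834 = 10078; less 20% loss, 10078 × 0.80 = 8062, or 4031 per group. Control risk 4%, risk ratio 0.667, two-sided alpha 0.04, 1:1 allocation.

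**Formula** (Pearson chi-square, no continuity correction), with n per group, p̄ the mean of p₁ and p₂, and z = 2.0537:

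Power = Φ{ [ |p₁ − p₂|√n − z√(2p̄(1 − p̄)) ] / √( p₁(1 − p₁) + p₂(1 − p₂) ) }

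**Step 1: the protocol's own figures.** p₁ = 0.04, p₂ = 0.04 × 0.667 = 0.02668, difference 0.01332, p̄ = 0.03334. The two square-root terms are 0.2539 and 0.2537.

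- n = 4031: (0.8457 − 2.0537 × 0.2539) / 0.2537 = 1.278, power 89.9%.
- n = 3038: (0.7342 − 0.5214) / 0.2537 = 0.839, power 79.9%.

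With a risk ratio of exactly 2/3 these become 90.0% and 80.0%. The arithmetic of 11.1 is correct.

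**Step 2: what the 90% requires.** It applies 4% to every control, Stage 1 included. Evaluable Stage 2 participants per arm: 7244 × 0.84 / 2 = 3042. Stage 1 by subtraction: 4031 − 3042 = 989, about 70% of 1417. The protocol gives no Stage 1 event rate, so the rates below are assumptions. The risk ratio is 0.667 in both stages.

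Example at a Stage 1 rate of 0: control risk = 3042 × 0.04 / 4031 = 3.02%; BCG risk = 3.02% × 0.667 = 2.01%; risk difference 1.0 point instead of 1.33.

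| Assumed Stage 1 control rate | Crude pooled power | Stage-stratified (Mantel-Haenszel) power |
|---|---|---|
| 0% | 79.6% | 80.0% |
| 0.1% | 80.0% | 80.3% |
| 0.5% | 81.3% | 81.5% |
| 1% | 82.8% | 83.0% |
| 2% | 85.6% | 85.6% |
| 4% | 89.9% | 89.9% |

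Stage 1 retention matters little. With 20% loss (1134 per arm) or 16% loss (1190 per arm), crude power is 80% at a rate of 0, 83% at 1%, and 86% or 87% respectively at 2%.

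**Step 3: false-positive cases, illustration only.** Suppose 0.5% or 1% of Stage 1 participants in both arms were wrongly counted as severe cases (4.9 or 9.9 per arm) and there were no true ones.

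- 0.5%: control (121.68 + 4.9) / 4031 = 3.14%; BCG (81.16 + 4.9) / 4031 = 2.14%; risk ratio 0.680, crude power 77.7%.
- 1%: 3.26% and 2.26%; risk ratio 0.692, crude power 75.8%.

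**The case against.** The strongest reply is that 11.1 settles the matter. Its last paragraph follows the pooled power statement, calls pooling of all outcomes the original plan, dates the change and gives reasons. Read in order, the 90% is the old plan, and what remains is stale text in 11.3. The harm would then need an analyst to ignore 11.1, and the power of a withdrawn analysis under assumed rates would be beside the point.

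Part of this stands. The last paragraph of 11.1 shows the sponsor's later intention, and a careful reader of that section would find it. But the power statement is written in the future tense and is not marked as superseded, whereas 11.4 does label its figures as the original calculation. Nor does this reading repair 11.3, the operative methods section, which comes later and orders the pooled COVID-19 analysis without qualification. The SAP was not available for this point; whichever way it goes, it must depart from one of the two sections.

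Further limits are fair:

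- The false-positive rates are not in the protocol, and a false severe case would need a qualifying illness as well as a false test. That step is not needed for the conclusion.
- The pooled-analysis sentence under secondary outcomes is too broad rather than wholly wrong, because it also covers febrile and respiratory illness, where pooling is kept.
- The power phrase in section 4.1 names no endpoint, but it sits in a paragraph about COVID-19 and reads that way. The synopsis makes no power claim; it only omits the restriction.

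**Conclusion.** The point holds, and the text should be fixed. Section 11.3 and the pooled power statement in 11.1 cannot both stand with the closing paragraph of 11.1. This rests on the wording alone and needs no assumption.

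The size does rest on assumed Stage 1 rates. If exposure was almost negligible, taken here as 0 to 0.5% severe COVID-19 in Stage 1 controls, pooling gives 80 to 81% power crude and 80 to 82% stage-stratified, against 80% for Stage 2 alone. The 90% is reached only if Stage 1 controls also had the full 4%.

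Only a secondary analysis is at issue. The confirmatory Stage 2 comparison, its stated 80% power, its alpha and the Stage 2-only interim analysis do not change.

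**What to change.** 1. **Section 11.3, both pooled-analysis paragraphs:** limit the 10078-participant analyses and the treatment-by-stage interaction to febrile or respiratory illness and other non-COVID-19 outcomes.
2. **Section 11.1:** delete the 8062-participant, 90% power statement for severe COVID-19 and the sentence placing it in the final report, or mark both as superseded in December 2021. The Stage 2 figure of 80% is then the only stated power for that outcome.
3. **Section 4.1:** remove the claim that pooling is critical for power.
4. **Section 4.1 and synopsis:** state that the meta-analysis covers non-COVID-19 outcomes only.

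If the sponsor does want a pooled COVID-19 analysis, the closing paragraph of 11.1 must change instead, the Stage 1 data must be cleaned, and the power must be recalculated with a realistic Stage 1 rate.

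The recommended change costs text only: no new data, no change to sample size or alpha. Its one visible price is that the best stated power for severe COVID-19 falls from 90% to 80%.
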